DOR will be calculated for the ITT population who achieve CR or PR. For such patients, DOR is defined as the number of days from the start date of PR or CR (whichever response is achieved first) to the first date that recurrent or progressive disease is objectively documented. In such cases, recurrent or progressive disease will be assessed relative to the smallest tumor burden measurements recorded since the start of protocol treatment.

DOR will be summarized descriptively using the Kaplan-Meier method. DOR will be right-censored for patients who achieve CR or PR based on the conventions described for PFS.

Progression-free Survival

PFS is defined as the number of months from the start date of protocol treatment to the earlier of disease progression or death due to any cause. Disease progression will be assessed using RECIST 1.1 and irRECIST for cohort 2. PFS will be based on the ITT patient population.

PFS will be right-censored for patients who met one or more of the following conditions:

- Patients with no baseline or post-baseline disease assessments unless death occurred prior to the first planned assessment (in which case the death will be considered a PFS event)
- Patients who initiate subsequent anti-cancer therapy in the absence of documented progression
- Patients who die or have disease progression after missing two or more consecutively scheduled disease assessment visits

- Patients who are last known to be alive and progression-free on or before the data cut-off date

The progression and censoring dates will be based on the conventions described in the May 2007 FDA Guidance for Industry, '*Clinical Trial Endpoints for the Approval of Cancer Drugs and Biologics*'. The primary analysis of PFS will be based on PFS events determined by the investigator. In addition, in the event of a positive study outcome, an additional assessment of tumor response and progression may be performed by an IRC blinded to investigator assessments.

PFS will be summarized descriptively using the Kaplan-Meier method. Median PFS and its corresponding 95% confidence interval will be reported. The PFS rate and its corresponding 95% confidence interval for at various landmark time points will also be estimated using the Kaplan-Meier method. Greenwood's formula will be used to calculate the standard errors of the Kaplan-Meier estimate and upper and lower limits of the 95% confidence interval. Similar analyses may be performed for additional landmarks.

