 - When no imaging/measurement is done at all at a particular time point, the patient is not evaluable (NE) at that time point.
 - If only a subset of lesion measurements are made at an assessment, usually the case is also considered NE at that time point, unless a convincing argument can be made that the contribution of the individual missing lesion(s) would not change the assigned time point response. This would be most likely to happen in the case of PD. For example, if a patient had a baseline sum of 50mm with three measured lesions and at follow-up only two lesions were assessed, but those gave a sum of 80 mm, the patient will have achieved PD status, regardless of the contribution of the missing lesion.
- 'Symptomatic deterioration': Patients with a global deterioration of health status requiring discontinuation of treatment without objective evidence of disease progression at that time should be reported as 'symptomatic deterioration'. Every effort should be made to document objective progression even after discontinuation of treatment. Symptomatic deterioration is not a descriptor of an objective response: it is a reason for stopping study therapy. The objective response status of such patients is to be determined by evaluation of target and non-target disease as shown in [Appendix 3 Table 1](#) and [Appendix 3 Table 2](#).

- In some circumstances it may be difficult to distinguish residual disease from normal tissue. When the evaluation of complete response depends upon this determination, it is recommended that the residual lesion be investigated (fine needle aspirate/biopsy) before assigning a status of complete response. FDG-PET may be used to upgrade a response to a CR in a manner similar to a biopsy in cases where a residual radiographic abnormality is thought to represent fibrosis or scarring.
- For equivocal findings of progression (e.g. very small and uncertain new lesions; cystic changes or necrosis in existing lesions), treatment may continue until the next scheduled assessment. If at the next scheduled assessment, progression is confirmed, the date of progression should be the earlier date when progression was suspected.
- Confirmation of response: In the event of complete or partial responses, efforts should be made to obtain a confirmatory scan (no sooner than 28 days later).

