2.2.2 Secondary endpoint(s)

Efficacy

- Duration of response (DOR), defined as the time from response criteria are first met for either complete response (CR) or partial response (PR), until the first date that

progressive disease (PD) is objectively documented, or until death (if death occurs within 9 weeks of the last evaluable scan), for subjects who achieve confirmed CR or PR.

- Progression-free survival (PFS), defined as the time from first dose of study treatment date to first documentation of objective progression or death due to any cause, whichever occurs first.
- Overall survival (OS), defined as the time from first dose of study treatment to death due to any cause.

Safety Endpoints

- Incidence of adverse events
- Deaths on study
- Discontinuations of study drug due to adverse events
- Changes in vital sign parameters
- Changes in hematology, chemistry, and other laboratory parameters
- ECG parameters
- ECOG performance status

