8.2 Analyses of Secondary Endpoints

8.2.1 PFS

Progression Free Survival (PFS) is defined as the time from the study treatment first dose to the earlier of disease progression or death due to any cause. Disease progression will be assessed using RECIST 1.1. The progression and censoring dates will be based on the May 2007 FDA Guidance for Industry, ‘*Clinical Trial Endpoints for the Approval of Cancer Drugs and Biologics*’. Determination rules for events or censored PFS is summarized in Table 2.

Table 2: Date of Event or Censoring for the Primary PFS analysis

Situation	Date of Event or Censoring	Outcome
Disease progression between scheduled disease assessments	Date of progression	Event
Death between scheduled disease assessment	Date of death	Event
Death before the first planned disease assessment at 6 weeks (plus 1 week window) without any disease assessment	Date of death	Event
No baseline disease assessments	Date of first dose	Censored
No post-baseline disease assessments without death before the first planned disease assessment	Date of first dose	Censored
Discontinuation of study treatment without progression (i.e., due to toxicity, withdrew consent, or lost to follow-up) and no further radiographic assessment ^a	Date of last radiological assessment	Censored
Alternate anticancer treatment started without documentation of disease progression beforehand ^b	Date of last radiological assessment prior to start of further anticancer treatment	Censored
Death or disease progression after missing two or more consecutively scheduled disease assessments ^c	Date of last radiological assessment without documented progression disease prior to death/progression	Censored
Patients who have not progressed and are alive	Date of last radiological assessment without documented progression disease	Censored

- For a patient who discontinues study treatment without PD and continues to have radiographic assessments, post-treatment radiographic assessments will be considered for PFS analyses according to the rules in this table.
- Alternate anticancer treatment interventions that are diagnostic (e.g. biopsy) or palliative (e.g., local radiation for painful nodule), as determined by medical review, will not routinely require censoring unless they are determined to interfere with the assessment of the patients’ disease status.

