8.2.2 Duration of response (DOR) and disease control rate (DCR)

Duration of Response (DOR) will be calculated for subjects who achieve confirmed CR or PR. For such subjects, DOR is defined as the time from response criteria are first met for either CR or PR, until the first date PD is objectively documented, or until death. DOR will be right-censored based on the same rules as described for PFS above.

DOR will be summarized descriptively and the median DOR will be estimated using the Kaplan-Meier method.

Swimmer plots will be provided depicting graphically the duration of response for patients who achieve complete response or partial response per RECIST 1.1 in each cohort. For Cohorts 2 and 3, swimmer plots of tumor response will also be provided per irRECIST criteria.

Disease control rate (DCR) is defined as the proportion of evaluable subjects who achieved BOR of CR or PR with any duration or SD with duration of at least 3 months (i.e., ≥ 3 months). The estimate of the DCR will be accompanied by one-sided and two-sided 95% Clopper-Pearson confidence intervals. Additionally, DOR and DCR will be derived and summarized based on the irRECIST criteria for Cohorts 2 and 3 subjects.

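### SAP Table 2 censors PFS and DOR at the last radiological assessment without requiring it to be evaluable, so a not-evaluable scan can extend progression-free follow-up

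*Protocol*

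**What the plan says.** SAP 8.2.1, Table 2, has four rows that censor PFS at a scan date:

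- Treatment stopped without progression and no further imaging: the last radiological assessment.
- Alternate anticancer treatment started first: "Date of last radiological assessment prior to start of further anticancer treatment".
- Death or progression after two or more consecutive missed assessments: "Date of last radiological assessment without documented progression disease prior to death/progression".
- Alive and not progressed: "Date of last radiological assessment without documented progression disease".

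No row or footnote says that the assessment must be evaluable. SAP 8.2.2 carries the rules over: "DOR will be right-censored based on the same rules as described for PFS above".

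Protocol Appendix 3 defines when a time point is NE. If nothing was imaged: "When no imaging/measurement is done at all at a particular time point, the patient is not evaluable (NE) at that time point". If imaging was partial: "If only a subset of lesion measurements are made at an assessment, usually the case is also considered NE at that time point". Appendix 3 Table 1 gives NE when target lesions are not all evaluated, non-target disease is not progressing and there are no new lesions.

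Two other places bear on the point. Protocol 11.5.1 lists among the censored "Patients who are last known to be alive and progression-free on or before the data cut-off date". SAP 2.2.2 counts a death as a DOR event only if "death occurs within 9 weeks of the last evaluable scan".

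**The concern.** A partly measured scan has a date and, if rated NE, no documented progression. It therefore meets the wording of all four rows and becomes the censoring date. Take a patient with stable disease at week 6 and an NE scan at week 12 who then withdraws. Table 2 read literally censors this patient at week 12, although the last assessment showing no progression was at week 6.

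This fits poorly with the protocol's description of the censored patient as last known to be progression-free. SAP 2.2.2 shows that its authors distinguish evaluable scans, but it uses the distinction only to decide which deaths count in DOR. SAP 8.1 handles NE only for ORR. At stake are the Kaplan-Meier summaries of PFS and DOR, including the 6-month PFS rate that SAP 8.2.1 names as an output.

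**Working it through.** The plan states no figure on this point, so there is none to reproduce. The check has three steps.

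**1. Shift per patient.** The input is the scan schedule in the footnote to SAP Table 2: every 6 weeks to week 24, then every 9 weeks, giving nominal scans at weeks 6, 12, 18, 24, 33, 42 and so on. Added time = week of the last scan − week of the last evaluable scan.

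| Trailing NE scan(s) | Censored, literal reading | Last evaluable | Added weeks |
|---|---|---|---|
| 6 | 6 | 0 (first dose) | 6 |
| 12 | 12 | 6 | 6 |
| 12 and 18 | 18 | 6 | 12 |
| 24 | 24 | 18 | 6 |
| 33 | 33 | 24 | 9 |
| 33 and 42 | 42 | 24 | 18 |

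A visit with no imaging at all is also NE, but it has no scan date and cannot move the censoring date. Only partly measured scans matter.

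**2. Direction.** The Kaplan-Meier estimate is S(t) = ∏(1 − d_j/n_j) over event times up to t. With the event rows unchanged, every d_j stays the same. A later censoring date can only raise n_j or leave it unchanged, so each factor, and hence S(t), is equal or higher. No assumption about who has NE scans is needed.

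**3. Size.** The documents give no NE rate, so this step rests on assumptions: exponential PFS with median 12, 18 or 26 weeks, NE probability 5%, 10% or 20% at each scan, loss to further scans 10% or 20% per visit, and 40,000 simulated patients per scenario. Selected results for the 26-week PFS rate:

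| True median (wk) | NE | Loss | Last scan | Last evaluable scan | Difference (points) | Patients moved |
|---|---|---|---|---|---|---|
| 12 | 5% | 10% | 0.256 | 0.254 | 0.2 | 1.3% |
| 12 | 20% | 20% | 0.279 | 0.259 | 2.0 | 9.3% |
| 18 | 5% | 10% | 0.402 | 0.400 | 0.2 | 1.5% |
| 18 | 10% | 20% | 0.407 | 0.399 | 0.8 | 5.3% |
| 18 | 20% | 20% | 0.421 | 0.402 | 1.9 | 10.9% |
| 26 | 20% | 20% | 0.547 | 0.530 | 1.7 | 12.3% |

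Over all 18 scenarios the difference is 0.2 to 2.0 points and 1% to 12% of patients change censoring date. The median, read on the scan grid (weeks 18, 24 and 33), is the same under both rules in every scenario.

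A second set of assumptions concentrates NE scans at the end: 5–10% at ordinary visits, 20–50% at the last visit, loss 10–15% per scan, true median 12–20 weeks. The difference is then 0.8 to about 3.6 points, and the median moved in one of 15 scenarios.

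For scale, the binomial standard error of a 26% rate, ignoring censoring, is √(0.26 × 0.74/60) = 5.7 points with 60 patients and √(0.26 × 0.74/30) = 8.0 points with 30.

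DOR was not simulated. The shift per responder is that in step 1, and the direction is that in step 2.

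**The case against.** The strongest reply is that Table 2 never mentions NE. The gap is an omission, and the protocol's phrase about patients last known to be progression-free favours a scan that shows status. Both documents also base the dates on a May 2007 FDA guidance that might fill the gap. It stands that no intention to count NE scans can be read into the SAP. But the guidance text is not in the documents, SAP 8.2.1 says Table 2 summarizes the rules, and a programmer following the table would include these scans.

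A reader might infer that an NE scan says nothing about progression. The documents do not support that. Under Appendix 3 Table 1, NE at a visit requires non-progressing non-target disease and no new lesions, so two of the three routes to progression were negative. Appendix 3 still allows progression to be called from a measured subset, and incomplete non-target assessment alone leaves PR or SD in place. NE is therefore narrow and carries partial evidence. It still does not establish freedom from target-lesion progression.

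A reader might also infer a material inflation of PFS. That is not supported either. The upper figure of about 3.6 points depends on an assumed 20–50% NE rate at last visits. The schedule of assessments expects all disease sites to be evaluated at each visit by the same method, and Appendix 3 gives steps for recovering a non-evaluable target lesion. That deteriorating patients have more NE scans is plausible, but the documents do not state it, and it affects only the size.

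Finally, nothing is decided on these curves. This stands, and it limits the weight of the point.

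**Conclusion.** The point holds as a minor defect in the censoring rule. Followed literally, the four scan-dated rows of Table 2 credit 6 weeks (9 after week 24) of follow-up per trailing NE scan for both PFS and DOR. With event rows unchanged, the curves can only be equal or higher. Under assumed NE rates, the 26-week PFS rate rises by about 0.2 to 2 points, or up to about 3.6 if NE scans cluster at last visits, and the median usually stays put. These sizes depend wholly on the assumed NE and loss rates and are small beside the sampling error of cohorts of 30 to 60.

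It would be wrong to conclude that the primary analysis is affected: SAP 8.1 counts NE as non-response in ORR. PFS and DOR are secondary, descriptive and summarized by single-arm cohort.

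**What to change.** In the four scan-dated rows of SAP Table 2, and so for DOR through SAP 8.2.2, replace the last radiological assessment with: *last evaluable radiological assessment (overall response other than NE) without documented progression; date of first dose if there is none*. The first-dose fallback matters only for PFS, because a confirmed responder already has an evaluable scan.

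The same edit should state whether an NE time point counts as missed in the two-missed-assessments row, and as no assessment in the no-post-baseline row. Otherwise NE scans are treated inconsistently. With stable disease at week 6, NE at weeks 12 and 18 and progression at week 24, no scan was skipped, so the patient stays an event at week 24 although the new wording treats those two scans as uninformative for censoring. If NE is made to count as missed, some events become censored, and the direction shown above no longer follows automatically.

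The cost is a phrase in each of four rows, a sentence on NE time points and an NE filter in the PFS and DOR programs. Follow-up becomes slightly shorter. A patient whose only post-baseline scan is NE is censored at first dose and contributes no follow-up, which is noticeable in a cohort of about 30.

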Appendix 3 Table 1: Overall response: patients with target +/-non-target disease.

Target lesions	Non-target lesions	New lesions	Overall response
CR	CR	No	CR
CR	Non-CR/non-PD	No	PR
CR	Not evaluated	No	PR
PR	Non-PD or not all evaluated	No	PR
SD	Non-PD or not all evaluated	No	SD
Not all evaluated	Non-PD	No	NE
PD	Any	Yes or No	PD
Any	PD	Yes or No	PD
Any	Any	Yes	PD

CR = complete response, PR = partial response, SD = stable disease, PD = progressive disease, and NE = inevaluable.

Appendix 3 Table 2: Overall response: patients with non-target disease only.

Non-target lesions	New lesions	Overall response
CR	No	CR
Non-CR/non-PD	No	Non-CR/non-PD ^a
Not all evaluated	No	NE
Unequivocal PD	Yes or No	PD
Any	Yes	PD

CR = complete response, PD = progressive disease, and NE = inevaluable

^a 'Non-CR/non-PD' is preferred over 'stable disease' for non-target disease since SD is increasingly used as endpoint for assessment of efficacy in some trials so to assign this category when no lesions can be measured is not advised.

FREQUENTLY ASKED QUESTIONS

What should be done if several unique lesions at baseline become confluent at a follow-up evaluation?

Measure the longest diameter of the confluent mass and record to add into the sum of the longest diameters.

How large does a new lesion have to be to count as progression? Does any small sub-centimeter lesion qualify, or should the lesion be at least measurable?

New lesions do not need to meet ‘measurability criteria’ to be considered valid. If it is clear on previous images (with the same technique) that a lesion was absent then its definitive appearance implies progression. If there is any doubt (because of the techniques or conditions) then it is suggested that treatment continue until next scheduled assessment when, generally, all should be clear. Either it gets bigger and the date of progression is the date of the first suspicion, or it disappears and one may then consider it an artifact with the support of the radiologists.

How should one lesion be measured if on subsequent exams it is split into two?

Measure the longest diameter of each lesion and add this into the sum.

Does the definition of progression depend on the status of all target lesions or only one?

As per the RECIST 1.1 guideline, progression requires a 20% increase in the sum of diameters of all target lesions AND a minimum absolute increase of 5 mm in the sum.

What is the criterion for a measurable lesion if the CT slice thickness is >5 mm?

RECIST 1.1 recommends that CT scans have a maximum slice thickness of 5 mm and the minimum size for a measurable lesion is twice that: 10 mm (even if slice thickness is <5 mm). If scanners with slice thickness >5 mm are used, the minimum lesion size must have a longest diameter twice the actual slice thickness.

What should we record when target lesions become so small they are below the 10 mm ‘measurable’ size?

Target lesion measurability is defined at baseline. Thereafter, actual measurements, even if <10 mm, should be recorded. If lesions become very small, some radiologists indicate they are ‘too small to measure’. This guideline advises that when this occurs, if the lesion is actually still present, a default measurement of 5 mm should be applied. If in fact the radiologist believes the lesion has gone, a default measurement of 0 mm should be recorded.

If a patient has several lesions which have decreased in size to meet PR criteria and one has actually disappeared, does that patient have PD if the ‘disappeared’ lesion reappears?

Unless the sum meets the PD criteria, the reappearance of a lesion in the setting of PR (or SD) is not PD. The lesion should simply be added into the sum. If the patients had had a CR, clearly reappearance of an absent lesion would qualify for PD.

When measuring the longest diameter of target lesions in response to treatment, is the same axis that was used initially used subsequently, even if there is a shape change to the lesion that may have produced a new longest diameter?

The longest diameter of the lesion should always be measured even if the actual axis is different from the one used to measure the lesion initially (or at different time point during follow-up). The only exception to this is lymph nodes: as per RECIST 1.1 the short axis should always be followed and as in the case of target lesions, the vector of the short axis may change on follow-up.

Target lesions have been selected at baseline and followed but then one of these target lesions then becomes non-evaluable (i.e. different technique used). What is the effect this has on the other target lesions and the overall response?

What may be done in such cases is one of the following:

(a) If the patient is still being treated, call the center to be sure that future evaluations are done with the baseline technique so at least SOME courses are fully evaluable

(b) If that is not possible, check if there IS a baseline exam by the same technique which was used to follow patients, in which case if you retrieve the baseline measures from that technique you will also retrieve the lesion's ability to be evaluated.

(c) If neither (a) nor (b) is possible then it is a judgment call about whether you delete the lesion from all forms or consider the impact of the lesion overall is so important that its status of being non-evaluable makes the overall response interpretation in-evaluable without it. Such a decision should be discussed in a review panel.

It is NOT recommended that the lesion be included in baseline sums and then excluded from follow-up sums since this biases in favor of a response.

What if a single non-target lesion cannot be reviewed, for whatever reason; does this negate the overall assessment?

Sometimes the major contribution of a single non-target lesion may be in the setting of CR having otherwise been achieved: failure to examine one non-target in that setting will leave you unable to claim CR. It is also possible that the non-target lesion has undergone such substantial progression that it would override the target disease and render patient PD. However, this is very unlikely, especially if the rest of the measurable disease is stable or responding.

A patient has a 32% decrease in sum cycle 2, a 28% decrease cycle 4 and a 33% decrease cycle 6. Does confirmation of PR have to take place in sequential scans or is a case like this confirmed PR?

It is not infrequent that tumor shrinkage hovers around the 30% mark. In this case, most would consider PR to have been confirmed looking at this overall case. Had there been two or three non-PR observations between the two time point PR responses, the most conservative approach would be to consider this case SD.

A patient has a lesion measurable by clinical exam and by CT scan. Which should be followed?

CT scan. Always follow by imaging if that option exists since it can be reviewed and verified.

A lesion which was solid at baseline has become necrotic in the center. How should this be measured?

The longest diameter of the entire lesion should be followed. Eventually, necrotic lesions which are responding to treatment decrease in size. In reporting the results of trials, you may wish to report on this phenomenon if it is seen frequently since some agents (e.g. angiogenesis inhibitors) may produce this effect.

If I am going to use MRI to follow disease, what is minimum size for measurability?

MRI may be substituted for contrast enhanced CT for some sites, but not lung. The minimum size for measurability is the same as for CT (10 mm) as long as the scans are performed with slice thickness of 5mm and no gap. In the event the MRI is performed with thicker slices, the size of a measurable lesion at baseline should be two times the slice thickness. In the event there are inter-slice gaps, this also needs to be considered in determining the size of measurable lesions at baseline.

Can PET–CT be used with RECIST?

At present, the low dose or attenuation correction CT portion of a combined PET–CT is not always of optimal diagnostic CT quality for use with RECIST measurements. However, if your site has documented that the CT performed as part of a PET–CT is of the same diagnostic quality as a diagnostic CT (with IV and oral contrast) then the PET–CT can be used for RECIST measurements. Note, however, that the PET portion of the CT introduces additional data which may bias an investigator if it is not routinely or serially performed.

Adapted from Eisenhower 2009 ([Eisenhauer, Therasse et al. 2009](#))

